ITT	Intention-to-treat
MRI	Magnetic Resonance Imaging
MS	multiple sclerosis
PP	Per Protocol
pwMS	people with multiple sclerosis
SAP	Statistical Analysis Plan

1 Introduction

This Statistical Analysis Plan (SAP) is based on the study protocol version 2.0 of August 30, 2020 and follows the guideline for statistical analysis plans (Gamble, et al., 2017)

Some points of the statistical methods and of the study design are already described in the study protocol. This Statistical Analysis Plan (SAP) aims to further specify the procedures and statistical methods applied during the final analysis of the study data.

1.1 Background and rationale

While Magnetic Resonance Imaging (MRI) plays a major role in the lives of people with multiple sclerosis (pwMS), studies have shown that MRI-specific knowledge in pwMS is limited. Moreover, poor knowledge was associated with negative feelings towards MRI (e.g. anxiety concerning MRI scan). Because information sources about MRI in MS for pwMS are not available, we designed and evaluated an evidence-based online educational platform about MRI in MS called "Understanding MRI in MS" (UMIMS). Based on a pilot study in n=104 subjects, an educational intervention was found to be feasible and effective. We hypothesize, that MRI-specific knowledge can be increased by using UMIMS and that, subsequently, negative feelings towards MRI will be reduced and shared decision-making competences increased.

1.2 Objectives

This study investigates whether the UMIMS programme increases MRI-specific risk knowledge compared to the control group.

2 Study Methods

2.1 Trial design

This randomized, controlled, double-blinded trial aimed to recruit n=120 pwMS. The intervention group received access to UMIMS. The control group received access to a specifically developed control website, which visually imitates UMIMS, and contains the standard information available by several MS self-help organisations. The change in MRI-specific knowledge assessed via the MRI-risk knowledge questionnaire (MRI-RIKNO) after the intervention was the primary outcome at 2 weeks.

2.2 Randomization

Permuted-block randomization was computer generated and performed by a statistician not involved in the conduct of the study. In a previous study, analysis of covariance did not reveal an influence of sociodemographic variables on MRI knowledge, therefore no stratification took place except for study site.

2.3 Sample size

It was calculated, that n=120 participants would have to be recruited to detect a difference of 16.3 vs 14.5 points in the MRI-RIKNO questionnaire with a power of 90% given an alpha of 5% and taking into account a 20% dropout rate.

For a detailed description of the sample size considerations please refer to the sample size section of the design paper (Schiffmann, et al., 2020).

2.4 Framework

UMIMS is planned to show superiority of the UMIMS intervention compared to the control group regarding the primary outcome change in the MRI-RIKNO questionnaire.

2.5 Statistical interim analyses and stopping guidance

No interim analyses were planned.

2.6 Timing of final analysis

The final analysis of the primary outcome will take place after the database has been reviewed for completeness and accuracy and database lock.

2.7 Timing of outcome assessments

The primary outcome was assessed two weeks after randomization. For the timing of other major outcomes of the UMIMS trial, see Table 1 in the design paper (Schiffmann, et al., 2020).

3 Statistical Principles

3.1 Confidence intervals and *P* values

All applicable statistical tests will be two-sided and will be performed using a 5% significance level. Analyses of secondary outcomes will be performed without adjustment for multiplicity. All confidence intervals presented will be 95% and two-sided.

3.2 Adherence and protocol deviations

At any point, patients in both groups were able to quit the study. Patients who withdrew from the study were asked whether they agreed to continue to fill in a limited set of questionnaires related to the primary study outcome. The data of non-adherent participants (e.g. who did not log use the website or those with missing questionnaires) will be included in the intention-to-treat analysis.

3.3 Analysis populations

3.3.1 Intention to treat Population (ITT)

The primary analysis population is the ITT (intention to treat) population. The ITT population consists of all patients randomized.

3.3.2 Per Protocol population (PP)

The Per Protocol population includes all patients randomized who have no major protocol violation.

Major protocol violations are any unapproved changes in the research study design and/or procedures that are within the investigator's control and not in accordance with the IEC/IRB -approved protocol that may affect the participant's rights, safety or well-being, or the completeness, accuracy and reliability of the study data.

Major protocol violation includes ineligible participants who were included in the trial by mistake, and those for whom the intervention or other procedure differed from that outlined in the protocol, or failure of consent process.

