5.3 Missing data

Altman (Altman, 2009) addressed that there is no ideal method to address missing data. Therefore, different common imputation techniques will be applied and reported with as well as without imputation techniques as suggested by Altman (Altman, 2009).

Multiple imputation techniques will be conducted in the sensitivity analysis.

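### Does the SAP leave it open whether participants who never used their allocated website belong to the Per Protocol set?

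*SAP*

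**What the plan says.** Section 3.3.2 defines the set in one sentence: "The Per Protocol population includes all patients randomized who have no major protocol violation". Its second paragraph explains a major violation as "any unapproved changes in the research study design and/or procedures that are within the investigator's control", where these depart from the approved protocol and may affect participants or the quality of the data. Its third paragraph says that major violation includes three things: ineligible people enrolled by mistake, "those for whom the intervention or other procedure differed from that outlined in the protocol", and a failed consent process.

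Section 3.2 deals with adherence: "The data of non-adherent participants (e.g. who did not log use the website or those with missing questionnaires) will be included in the intention-to-treat analysis". It does not mention PP. Section 3.3.1 makes ITT, meaning all patients randomized, the primary analysis population.

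Sections 5.2.1 (primary outcome), 5.2.2 (secondary outcomes), 5.4 (additional analyses) and 5.5 (harms) do not mention PP. Section 5.3 says "Multiple imputation techniques will be conducted in the sensitivity analysis" and ties no analysis to PP either.

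**The concern.** The investigator-control limit appears in the second paragraph of 3.3.2 and is not repeated in the third. Someone who was given access and chose not to use it is not a departure the investigator controls, so the second paragraph keeps that person in PP. The third paragraph, read on its own, could treat the same person as having had a different intervention and remove them. A missed questionnaire could likewise be read as a procedure that differed. Section 3.2 names both groups as non-adherent but places them only in the ITT analysis.

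For a self-directed website, non-use is the main adherence question. If a PP result were reported, two analysts might form different sets, and with no analysis assigned to PP, the choice of set and outcome might be made once results by arm are known.

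**Working it through.** **1. The plan's own figures (context only).** Section 2.3 gives N = 120, a difference of 16.3 − 14.5 = 1.8 points, 90% power and 5% alpha, "taking into account a 20% dropout rate". Section 3.1 makes tests two-sided. The SAP states no SD and refers to the design paper, so N cannot be reproduced from the SAP alone. Assuming 1:1 allocation and an SD of 2.7:

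- n per arm = 2 × (1.960 + 1.282)² × 2.7² / 1.8² = 47.3, rounded up to 48
- total evaluable = 2 × 48 = 96
- with dropout, 96 / (1 − 0.20) = 120

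An SD of 2.5 gives 103, 2.8 gives 128 and 3.0 gives 148. The PP question does not depend on any of this.

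**2. Head counts if the reading were open.** The SAP gives no rate of non-use, so the rates below are assumptions.

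| Assumed non-use | Non-users, 120 × rate | PP if kept in | PP if left out |
|---|---|---|---|
| 5% | 6 | 120 | 114 |
| 10% | 12 | 120 | 108 |
| 20% | 24 | 120 | 96 |
| 30% | 36 | 120 | 84 |

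The last two columns are before any other exclusion. The dropout allowance is 0.20 × 120 = 24 participants. It is a planning figure, not a count of people whose PP status is in doubt. Sections 3.2 and 4.3 also say that those who withdrew were asked to go on completing questionnaires for the primary outcome.

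**3. The two paragraphs of 3.3.2 side by side.**

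- The second paragraph has the form of a definition. The third opens with the word *includes* and gives instances, which are ordinarily read within the definition they illustrate.
- The two items beside the disputed phrase, mistaken enrolment and failed consent, are errors of the study team. In that company the phrase most naturally means that the wrong intervention or procedure was delivered.

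**4. What was allocated.** Section 2.1 says that each group received access to its website. Section 5.1 places t1 after two weeks of access. The SAP sets no minimum use. A participant who had access and did not log in received what was allocated, so even the third paragraph taken alone does not clearly exclude that person. Section 3.2 calls such participants non-adherent; it does not call them major violators.

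**5. Missing t1 questionnaires.** The primary model in 5.2.1 uses one change score per participant. Without a t1 score there is no change score, so in an analysis of observed data that person adds nothing to the primary comparison whether labelled in or out of PP. Missing data have their own section, 5.3.

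**6. Which planned results use PP.** None is named in sections 5.2 to 5.5. The primary result rests on everyone randomized and is the same under either reading.

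**The case for a change.** The strongest case for the concern is that the SAP sets out to specify the analysis further than the protocol does, defines a PP set itself, and yet never says whether the commonest form of non-adherence to a website puts someone outside it. The reconciling reading has to be inferred. Contrasting PP with an ITT analysis that expressly keeps non-adherent participants might even suggest that PP leaves them out. One sentence would have settled it.

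Part of this stands. The status of non-users is not stated outright, and no section assigns an analysis to PP; the second is the sounder criticism. What does not stand is the stronger claim that the two paragraphs conflict. They are ambiguous, and both the form of the text and the description of the allocation favour one reading.

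The two halves of the concern also weaken each other: if no planned analysis uses PP, its membership alters no planned result. Harm would need an unplanned PP analysis and a choice of set made with results by arm in view, and nothing in the SAP points to either. The introduction notes that some methods are described in the protocol, which was not available here, so a use for PP may be stated there.

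**Conclusion.** No change is called for. This is a gap in detail that a competent analyst fills sensibly: keep non-users in PP, since they were given the allocated access, and treat any PP run as supportive. An explicit sentence would be tidier, but it would replace no wrong rule or method.

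The effect on the primary result is nil, because that analysis includes all randomized patients whatever their use of the website. No magnitude for a PP estimate can be derived from the SAP; the range of 6 to 36 participants is only 120 multiplied by assumed rates.

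The conclusion rests on two things: reading the third paragraph of 3.3.2 as examples within the definition, and the absence from the SAP of any analysis whose conclusion depends on PP. If a PP result were to carry weight in the trial's conclusions, the membership rule would matter more.

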3.3.3 Evaluated for Safety Set (EFS)

All randomized patients will be included into the Evaluated for Safety (EFS) set.

4 Trial Population

4.1 Eligibility

The number of ineligible participants recruited, if any, will be reported, with reasons for ineligibility.

4.2 Recruitment

The CONSORT diagram in Figure 1 of the design paper will be updated with the actual recruitment figures.

4.3 Withdrawal/follow-up

Patients who withdrew from the study were asked whether they agree to continue to fill in a limited set of questionnaires related to the primary study outcome. We inquired causes for study withdrawal and will report those in case of disclosure to clarify whether there are any differences between the intervention and control groups.

4.4 Baseline patient characteristics

Available baseline data consists of demographic data, medical history, and clinical information including, among others, information on symptom onset, year of diagnosis, level of disability and experience with MRI.

Categorical data will be summarised by numbers and percentages. Continuous data will be summarised by mean, SD, median, IQR and range. Number of available observations and number of missing observations will be presented.

5 Analysis

5.1 Outcome definitions

The primary endpoint is MRI-risk knowledge measured by the MRI-risk knowledge questionnaire 2.0 (MRI-RIKNO) (11). It comprises n=14 items (maximum score of n=22) concerning basic neuroanatomy and lesion knowledge, the MRI procedure and the meaning of MRI for diagnosis, prognosis and treatment control. MRI-risk knowledge will be assessed twice during the trial: t0 (allocation) and t1 (after a 2-week-access to the intervention or control website). The primary endpoint is change of MRI-RIKNO score from baseline to t1.

5.2 Analysis methods

5.2.1 Primary outcome

The primary outcome will be analysed as change from baseline with the baseline value as covariate and random group as fixed factor in a linear mixed model with center as random intercept to map the stratified randomisation scheme. This is a model refinement from

the originally intended ANCOVA model in the design paper, taking into account the recommendations of Kahan et al (Kahan & Morris, 2013) (Kahan & Morris, 2012) for the analysis of stratified randomised trials.

5.2.2 Secondary outcomes

The secondary outcomes will be reported according to their respective scale.

The continuous outcomes

- Emotions and attitude towards MRI, assessed using the validated questionnaire "MRI emotions and attitude" (MRI-EMA) at t0, t1 and t2
- Perceived involvement in decisional encounters concerning MRI results and their consequences, evaluated with the Multifocal Approach to Sharing in Shared Decision Making (MAPPIN'SDM) evaluation at t2
- Quality of life (QoL), assessed using the subscales of the HAmburg QUAlity of life questionnaire in MS (HAQUAMS) using subscales fatigue, cognition, communication and mood at t3

will be analysed using linear mixed models with time and random group and their interaction term as fixed effects and center as random effect. The binary and ordinal outcomes "decisions on future MRIs and treatment changes as well as acceptance of the intervention, assessed from patients using a standardised questionnaire immediately at t2 and t3", and "Autonomy preference, assessed using the Control Preference Scale (CPS) at t0, t1 and t2" will be analysed using generalised logistic linear mixed models with the same covariate structure as above.

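### The HAQUAMS comparison at t3 is adjusted for center only; prespecifying baseline disability as a covariate would be a modest, almost free gain in precision

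*SAP*

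**What the plan says.** In SAP section 5.2.2 the quality-of-life outcome is "assessed using the subscales of the HAmburg QUAlity of life questionnaire in MS (HAQUAMS) using subscales fatigue, cognition, communication and mood at t3". No other visit is listed for it there. Together with the other continuous secondary outcomes it is to be analysed by "linear mixed models with time and random group and their interaction term as fixed effects and center as random effect". Center is the only adjustment, and no patient-level baseline covariate is named.

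Three other places bear on this:

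- Section 5.2.1 models the primary outcome as "change from baseline with the baseline value as covariate and random group as fixed factor", so the plan already accepts baseline adjustment in principle.
- Section 4.4 states that the baseline data include "information on symptom onset, year of diagnosis, level of disability and experience with MRI".
- Section 2.2 stratifies randomisation by study site only. Its reason is that sociodemographic variables did not influence MRI knowledge, which concerns the primary outcome and not quality of life.

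Section 2.7 refers to a table in the design paper for the timing of the other outcomes. That table is not part of the SAP text.

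**The concern.** Fatigue, cognition, communication and mood in people with MS can be expected to vary with the severity of their disease. If they do, the spread of disability within each arm adds to the residual variance of the t3 scores, and a chance difference in disability between the arms is left in the estimate. Disability is recorded at baseline, yet the model for this outcome does not use it.

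The model sentence also does not suit the outcome as listed. Time and time-by-group terms need at least two visits. The sentence fits MRI-EMA, which is listed at t0, t1 and t2, but not an outcome listed at t3 alone. It therefore has to be rewritten for HAQUAMS in any case, and the covariate can be settled in the same edit. If it is left open until the data are unblinded, any later adjustment for an observed imbalance will look data-driven.

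**Working it through.** **1. The model with one visit.** The listed fixed effects are intercept, group, time and time × group. With a single visit the time column is constant and equals the intercept, and the interaction column equals the group column. The design matrix has rank 2 of 4. What remains is intercept and group, with center as random intercept.

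**2. The plan's own figure.** Section 2.3 gives N = 120 for 16.3 vs 14.5 points (difference 1.8), 90% power, alpha 5% and 20% dropout; section 3.1 makes tests two-sided. No SD is stated, so 120 cannot be reproduced from the SAP alone. Allowing for dropout, 120 × 0.8 = 96, or 48 per arm if allocation is 1:1 (assumed). The implied SD is 1.8 × √(48/2) / (1.960 + 1.282) = 2.72, and 96/0.8 = 120 is consistent with it. This calculation is for the primary outcome. It is used here only to supply 96 completers, and the SAP does not state retention at t3.

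**3. Effect of a covariate.** Let r be the correlation between the baseline covariate and the t3 subscale within arms. The SAP gives no value, so a range is assumed.

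- Residual variance is multiplied by 1 − r².
- The standard error of the group difference, in SD units, is √(2/48) × √(1 − r²), which is 0.204 without a covariate.
- The equivalent unadjusted sample size is 96/(1 − r²).
- The difference detectable with 80% power is (1.960 + 0.842) × the standard error.

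| Assumed r | Variance reduction | SE (SD units) | Equivalent N (gain) | Detectable at 80% power | Power for 0.5 SD |
|---|---|---|---|---|---|
| 0 | 0% | 0.204 | 96 | 0.57 SD | 69% |
| 0.2 | 4% | 0.200 | 100 (+4) | 0.56 SD | 71% |
| 0.3 | 9% | 0.195 | 105.5 (+9.5) | 0.55 SD | 73% |
| 0.5 | 25% | 0.177 | 128 (+32) | 0.50 SD | 81% |

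The power column uses the normal approximation.

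**4. A smaller effect.** Two weeks of website access may move quality of life less than 0.5 SD. For 0.2 SD with 48 per arm (noncentral t), power is 16% unadjusted and 17% to 20% for r = 0.3 to 0.5. Adjustment does not rescue the power for an effect of that size; it narrows the interval.

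**5. Chance imbalance.** The standardised difference in baseline disability between arms has standard error 0.204, so its 95% range is about ±1.96 × 0.204 = ±0.40 SD. At r = 0.3 to 0.5 this carries up to 0.12 to 0.20 SD into the unadjusted t3 difference. The unadjusted standard error already allows for this. Adjustment removes it from the estimate.

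**The case against.** The strongest reply is that this is a preference about efficiency and not an error. A randomised comparison without prognostic covariates is unbiased and its intervals have correct coverage. This stands.

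A reader might nevertheless infer that an imbalance in disability would bias the t3 result, or that the secondary outcomes are analysed without any adjustment. The SAP supports neither reading. Allocation is random, and center, the only stratification factor, is in the model. The contrast with section 5.2.1 is also not exact, because the primary model adjusts for the same scale at baseline, whereas here only a related measure is known to exist.

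The gain does rest on an r that the SAP does not give. At 0.2 it is worth about 4 patients, and nothing shows that disability predicts all four subscales equally well.

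A reader might extend the point to shared decision-making, which is "evaluated with the Multifocal Approach to Sharing in Shared Decision Making (MAPPIN'SDM) evaluation at t2", with the t0 Control Preference Scale as covariate. The SAP does not support that step: autonomy preference and perceived involvement in an actual encounter are different constructs, and nothing in the text shows that one predicts the other.

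Finally, HAQUAMS may have been completed at t0 as well. The time terms in the model hint at more than one visit, and section 2.7 defers timing to the design paper. So the point holds for the outcome as section 5.2.2 lists it, and the fix must allow for a t0 score.

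**Conclusion.** The point holds as a modest improvement for HAQUAMS. As listed, the outcome has one visit, the time and interaction terms cannot be estimated, and the analysis is a valid, unbiased comparison adjusted for center only. Prespecifying baseline disability would cut residual variance by 4% to 25% for an assumed r of 0.2 to 0.5, equivalent to about 4 to 32 patients. This rests on 96 completers at t3, 1:1 allocation and a linear relation between disability and the subscale. At r of 0.3 or less the gain is small, with a standard error less than 5% lower. HAQUAMS is a secondary outcome, and section 3.1 tests secondary outcomes without multiplicity adjustment. The primary analysis and its conclusion are not affected.

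**What to change.** In section 5.2.2, take HAQUAMS out of the time-by-group sentence and give it its own model: each t3 subscale as response, group and prespecified baseline level of disability (section 4.4) as fixed effects, and center as random intercept. State the disability measure and the form in which it enters. If HAQUAMS was also completed at t0, say so and use the t0 subscale score as the covariate instead. Add a simple rule for missing covariate values, such as filling in the baseline mean.

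The cost is SAP wording and about one degree of freedom if disability enters linearly. No new data are needed if disability is the covariate.

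### The secondary models for repeatedly measured outcomes contain no patient-level term, so their group-by-time and visit-averaged tests have wrong standard errors

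*SAP*

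**What the plan says.** SAP Section 5.2.2 sets one model for the continuous secondary outcomes, which "will be analysed using linear mixed models with time and random group and their interaction term as fixed effects and center as random effect". For outcomes on a binary or ordinal scale, it says that they "will be analysed using generalised logistic linear mixed models with the same covariate structure as above".

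The same section lists the visits:
- MRI-EMA: t0, t1 and t2.
- Autonomy preference: "assessed using the Control Preference Scale (CPS) at t0, t1 and t2".
- Decisions on MRI and treatment, and acceptance of the intervention: t2 and t3.
- MAPPIN'SDM: t2 only.
- HAQUAMS subscales: t3 only.

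Section 5.2.1 explains what center is for. In the primary model it enters as "center as random intercept to map the stratified randomisation scheme". Section 3.1 sets two-sided 5% tests and 95% confidence intervals, with no multiplicity adjustment for secondary outcomes. Section 1.1 states the hypothesis behind MRI-EMA, namely that "negative feelings towards MRI will be reduced and shared decision-making competences increased".

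**The concern.** A model with time and a group-by-time interaction has one row per patient and visit. Rows from the same patient are correlated, and something in the model must represent that. Here the only random effect named is center, which reflects the stratified randomisation and does not identify the patient. The SAP gives no patient intercept, residual covariance by patient, GEE or robust variance.

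The direction of the error depends on the contrast reported, and Section 5.2.2 does not name one. A difference between arms in change over time is a within-patient quantity, and ignoring positive correlation makes its standard error too large. A group effect averaged over visits is a between-patient quantity, and its standard error becomes too small. The same fitted model can therefore miss a real reduction in negative feelings towards MRI, or give a spuriously significant average difference, depending on which coefficient is read.

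**Working it through.** **Plan's own figure.** The SAP gives no power or precision for the secondary outcomes, so there is none to reproduce. The number of patients comes from Section 2.3: 120 × (1 − 0.20) = 96 evaluable, or 48 per arm with equal allocation.

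**Assumptions not in the SAP.** Compound symmetry with within-patient correlation ρ, outcome SD = 1, complete data, a negligible center effect, and a true difference in change of 0.5 SD for the power figures. The main range is ρ = 0.5 to 0.7, with 0.3 shown as a lower value.

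**Linear model, group difference in change from t0 to t1 (n = 48 per arm).**
- SE as written: √(4/n) = √(4/48) = 0.289, so the 95% CI half-width is 1.96 × 0.289 = 0.57 SD.
- True SE: √(4(1−ρ)/n).
- Ratio of the two: 1/√(1−ρ).
- Actual type I error: 2(1 − Φ(1.96 × ratio)).
- Power as written: 1 − Φ((0.566 − 0.5)/true SE). Power with the correct SE: Φ(0.5/true SE − 1.96).

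| ρ | True SE | SE ratio | Type I error | Correct half-width (SD) | Power as written | Power, correct SE |
|---|---|---|---|---|---|---|
| 0.3 | 0.242 | 1.20 | 1.9% | 0.47 | 39% | 54% |
| 0.5 | 0.204 | 1.41 | 0.56% | 0.40 | 37% | 69% |
| 0.6 | 0.183 | 1.58 | 0.19% | 0.36 | 36% | 78% |
| 0.7 | 0.158 | 1.83 | 0.03% | 0.31 | 34% | 88% |

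**Joint 2-df interaction over t0, t1 and t2.** Type I error is P(χ²₂ > 5.991/(1−ρ)), which gives 1.4%, 0.25%, 0.06% and 0.005% at ρ = 0.3, 0.5, 0.6 and 0.7.

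**Group effect averaged over two post-baseline visits.** The SE is understated by √(1+ρ), and type I error is 2(1 − Φ(1.96/√(1+ρ))). At ρ = 0.3, 0.5, 0.6 and 0.7 the factor is 1.14, 1.22, 1.26 and 1.30, and the error is 8.6%, 11.0%, 12.1% and 13.3%.

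**Simulation checks, linear model.**
- With 20,000 trials at ρ = 0.5/0.6/0.7, null rejection of the interaction was 0.61%/0.19%/0.04%. Power was 38%/36%/34% as written, against 69%/79%/88% for a paired-change test. The two-visit average rejected in 11.1%/11.9%/13.6% of null trials, and a single-visit group difference in 5.3%/5.0%/5.2%.
- A separate simulation (96 patients, three visits, three centers assumed, 4,000 runs) compared the 2-df test as written with a within-patient analysis. At ρ = 0.3/0.5/0.7 the first rejected in 1.5%/0.35%/0.03% of null trials and the second in 5.1%/4.7%/5.2%.

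**Simulation, binary logistic model** (20,000 trials per setting, response 30% or 50%, latent correlation 0.5 or 0.7, which is a binary correlation of about 0.32 to 0.49).
- Interaction type I error: 1.7% falling to 0.6% as written, against 5.1% to 5.3% with patient-clustered variance.
- Two-visit average: 9% to 11% as written, against 5.1% to 5.3%.
- Power for a shift from 30% to 55% in one arm only, latent correlation 0.5/0.7: 38%/36% as written, against 54%/65%.
- Power for a shift from 50% to 75% in one arm only, latent correlation 0.5/0.7: 45%/44%, against 61%/72%.

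Ordinal models were not computed.

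**The case against.** The strongest reply is that the SAP is silent here and not wrong. It names center as a random effect without saying that it is the only one, and in a linear mixed model a by-patient residual covariance is specified separately from the random effects. The analyst may well intend one. That limits the finding to the model as stated, but it does not rescue the text. Section 5.2.2 spells out the random part of the model, and adding a patient term after the data are seen would be an undocumented choice. The reply is weaker still for the logistic models, which have no residual covariance of that kind by default.

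A second reply is that the decision and acceptance items might not each be asked at both visits. Section 2.7 leaves the timing table to the design paper. The plain reading of Section 5.2.2 puts them at t2 and t3, but MRI-EMA and the Control Preference Scale are the firmest cases.

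Third, the power loss depends on the effect assumed. At 0.8 SD, the test as written still has about 83%, 87% and 93% power at ρ = 0.3, 0.5 and 0.7. Likewise, a rough doubling of false positives for the averaged effect needs ρ of about 0.5 or more. Both points are fair and mark the range of the figures. Only ρ = 0, which is implausible for one person answering the same questionnaire repeatedly, removes the error.

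Finally, the stakes are secondary: no primary conclusion changes, and the error in the interaction is conservative. That also stands.

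**Conclusion.** The concern holds and should be fixed before the analysis. Fitted as stated, the model gives wrong standard errors, and confidence intervals without 95% coverage, for the group-by-time and visit-averaged contrasts of every outcome measured more than once.

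The contrast that the model most directly offers, the difference between arms in change, is tested too conservatively. Under the stated assumptions, a moderate effect on MRI-EMA would more likely be missed than found. A visit-averaged group effect, if that is what gets reported, is anti-conservative.

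Not affected are the primary outcome (one change score per patient), MAPPIN'SDM and HAQUAMS (one listed visit each), and a group difference at a single visit with complete data. The sizes rest on assumed correlations and, for power, on an assumed effect; the existence and direction of the error require only positive within-patient correlation.

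**What to change.** In Section 5.2.2, for each outcome measured more than once:
- Keep center and add a patient random intercept nested in center. For MRI-EMA, an unstructured within-patient residual covariance is an alternative.
- Name the contrast that will be read as the treatment effect: for example, the group difference in change from t0 for MRI-EMA and the Control Preference Scale, and the group difference at each visit for the t2/t3 items.
- For the binary and ordinal outcomes, say whether a patient intercept or a marginal approach (GEE or patient-clustered robust variance) is used. With two or three observations per patient the intercept model may be unstable, and its odds ratio is patient-specific. The marginal approach gives a population-averaged odds ratio.

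Fit MAPPIN'SDM and HAQUAMS without time terms, since each has one listed visit.

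The cost is two or three sentences and a small change in model code, with no new data. The one real decision is which odds ratio to report in the logistic models.

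### The repeated-measures model for MRI-EMA names no within-patient term and makes inefficient use of the baseline; CPS inherits the same structure

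*SAP*

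**What the plan says.** SAP section 5.2.2 lists MRI-EMA as "assessed using the validated questionnaire 'MRI emotions and attitude' (MRI-EMA) at t0, t1 and t2", so each patient gives up to three responses, one of them at baseline. The continuous secondary outcomes "will be analysed using linear mixed models with time and random group and their interaction term as fixed effects and center as random effect". No other term is given: no t0 covariate, no equal-means constraint at t0, no patient effect and no residual covariance structure. The section also does not say which contrast is the treatment effect.

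CPS, also measured at t0, t1 and t2, is to be analysed with "generalised logistic linear mixed models with the same covariate structure as above".

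The primary outcome is handled differently in section 5.2.1: "The primary outcome will be analysed as change from baseline with the baseline value as covariate", "in a linear mixed model with center as random intercept". That model has one change value per patient.

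Section 3.1 states: "All confidence intervals presented will be 95% and two-sided".

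**The concern.** There are two separate issues.

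1. **Use of baseline.** Randomisation makes the arm means at t0 equal in expectation. The section 5.2.2 model leaves them free. A treatment effect read from the interaction then uses t0 by plain subtraction, and one read as the difference at a visit ignores t0. Either costs precision compared with adjustment, which the SAP already adopts for the primary outcome.

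2. **Within-patient correlation.** A center intercept alone is adequate for one value per patient, as in section 5.2.1. With three values per patient it treats responses from the same person as independent, given center, so model-based standard errors can be wrong. The direction of the error depends on the contrast reported, which the SAP does not fix.

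MRI-EMA carries the hypothesis in section 1.1 that negative feelings towards MRI will fall. An interval that is avoidably wide, or that lacks its stated coverage, weakens that secondary result.

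**Working it through.** The SAP gives no precision or power figure for MRI-EMA, so there is none to reproduce. The check compares the stated model with the alternative.

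**Inputs from the SAP.** N = 120 and, from section 2.3, "taking into account a 20% dropout rate", so 120 × 0.8 = 96 evaluable; two-sided 5% tests and 95% intervals (section 3.1); three MRI-EMA visits (section 5.2.2).

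**Assumptions not in the SAP.** 1:1 allocation (48 per arm); the 20% dropout applied to MRI-EMA; equal variances and compound symmetry with within-patient correlation ρ = 0.3, 0.5 or 0.7; effects of 0.4, 0.5 and 0.6 SD.

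**Step 1: within-patient correlation modelled.** In units of the outcome variance, the per-arm variance factors are:
- change from t0: 2(1 − ρ)
- difference at one visit: 1
- baseline-adjusted difference: 1 − ρ²

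The standard error is √(2 × factor / 48). Power is from the noncentral t distribution.

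| | ρ = 0.3 | ρ = 0.5 | ρ = 0.7 |
|---|---|---|---|
| Change factor | 1.40 | 1.00 | 0.60 |
| Adjusted factor | 0.91 | 0.75 | 0.51 |
| Variance ratio, change to adjusted, 2/(1 + ρ) | 1.54 | 1.33 | 1.18 |
| Variance ratio, visit difference to adjusted, 1/(1 − ρ²) | 1.10 | 1.33 | 1.96 |
| Excess variance of the better contrast | 10% | 33% | 18% |
| Equivalent n per arm, 48(1 − ρ²)/min(1, 2(1 − ρ)) | 43.7 | 36.0 | 40.8 |
| Power at 0.5 SD: change | 54% | 68% | 88% |
| Power at 0.5 SD: visit difference | 68% | 68% | 68% |
| Power at 0.5 SD: adjusted | 72% | 80% | 92% |
| Gain over the better contrast, points | 4.1 | 12.0 | 4.5 |

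The gain at other settings, in the same order of ρ, is 3.7/11.8/6.8 points at 0.4 SD and 3.3/9.0/1.9 at 0.6 SD. At 0.5 SD it is 3.7/10.5/2.8 with no dropout (60 per arm) and 4.1/12.4/5.5 with 30% dropout (42 per arm).

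**Step 2: center as the only random effect.** Center effects are set to zero here. The fit has six arm-by-visit cells with residuals treated as independent.
- Model standard error of the change contrast: √(4/48) = 0.289 SD at every ρ.
- True standard error: √(4(1 − ρ)/48) = 0.24, 0.20, 0.16 SD.
- Ratio, 1/√(1 − ρ): 1.20, 1.41, 1.83.

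Simulation (8,000 trials per ρ and effect, 48 per arm) gave for this contrast:
- coverage of the nominal 95% interval: 98.1%, 99.4%, 99.9%
- type I error: 1.9%, 0.6%, 0.1%
- power at 0.5 SD: 39%, 38%, 34%

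**Step 3: other contrasts under the same literal fit.** A single-visit difference compares different patients at one time, so its standard error is about right. A group effect averaged over all three visits goes the other way: true variance divided by model variance is 1 + 2ρ = 1.6, 2.0, 2.4, so the type I error is P(|Z| > 1.96/√(1 + 2ρ)) = 12%, 17%, 21%.

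**CPS.** Both omissions carry over in kind. The figures above are for a continuous outcome, and none is claimed for CPS.

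**The case against.** Keeping t0 as a response with time, group and their interaction is a standard, valid longitudinal analysis. It gives unbiased contrasts and retains patients with partial data. Treating a three-visit secondary outcome differently from the primary outcome contradicts nothing. The efficiency gain is modest unless ρ is near 0.5, and ρ, the effect size and the dropout are all assumed.

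On the missing patient term, the sentence covers three outcomes at once. Two of them are listed at a single visit, so it may be shorthand, and few statisticians would fit three visits without within-patient correlation. The structure that CPS copies may likewise mean the fixed terms only.

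What stands: the baseline point concerns precision, not validity, and the step 2 figures apply only if the model is fitted as written. What does not stand: the plan names its random effect, and it is center, so the reader should not have to guess at another. Even if a patient effect was intended, the baseline loss in step 1 remains. Partial data need not be given up, because the constrained form keeps t0 as a response.

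**Conclusion.** The concern holds on both counts and should be acted on. As written, the model for MRI-EMA, and for CPS by reference, lacks a within-patient term and does not use the baseline efficiently.

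Under the assumptions in the working, the baseline omission costs 10% to 33% in variance against the better available contrast, or about 4 to 12 points of power at 0.5 SD. If the text is followed literally, the change-from-t0 interval over-covers and its power falls to 34% to 39%, while an effect averaged over the visits would reject too often. Neither gives the 95% interval or 5% test of section 3.1.

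Point estimates remain unbiased, the outcomes are secondary, and the primary analysis is unaffected.

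**What to change.** For MRI-EMA, adopt one of two forms in section 5.2.2:

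- **Covariate form.** Responses at t1 and t2; fixed effects group, time, group-by-time, the t0 value and t0-by-time; random effects patient and center.
- **Constrained form.** Responses at t0, t1 and t2, with arm means set equal at t0, a stated within-patient covariance, and center as random effect.

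In either case, name the group difference at t1 and at t2, each with its 95% interval, as the reported effects.

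Use the same structure for CPS. State that under the covariate form its odds ratio is conditional on the t0 value, and that with a patient random effect it is also conditional on that effect. Any binary or ordinal item collected at both t2 and t3 also needs a patient term.

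The cost is SAP wording only, with no new data. The covariate form needs a simple baseline imputation for a patient without a t0 value; the constrained form does not.
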